16.0 REVISION HISTORY

REV	Description of Change	Date
A	Initial release to FDA	11 Apr 2019
B	Release of IDE-approved copy. In section 7.3.3, updated mathematical expression of null hypothesis from $H_0: \mu < PG$ to $H_0: \mu \leq PG$ upon recommendation from FDA. Added J-Score definition to section 14.0 and reference to section 15.0.	22 May 2019
C	Added 30-Day (± 7 days) assessment to collect 30-day MACE as part of secondary objectives for the study. Updated Figure 4 and Table 4 to reflect 30-Day assessment. Updated NCT number. Added abbreviations of CHF and NYHA to Abbreviations table. Updated exclusion criterion 7 in synopsis to reflect corresponding change in body of protocol. Updated exclusion criterion 2 to be consistent with protocol definition of an MI. Definition of Severe CHF added to exclusion criterion 8. References to "Angiographic Core Laboratory Guidelines" changed to "instructions provided by the core laboratory" Clarified reference to transient sinus bradycardia to heart rate ≤ 50 bpm. Added definition of New York Heart Association (NYHA) Heart Failure classification. Minor grammatical corrections to entire document.	04 Feb 2020

APPENDIX A: GUIDELINER CATHETER INVESTIGATIONAL INSTRUCTIONS FOR USE

APPENDIX B: TRAPLINER CATHETER INVESTIGATIONAL INSTRUCTIONS FOR USE

APPENDIX C: TURNPIKE CATHETER INVESTIGATIONAL INSTRUCTIONS FOR USE

APPENDIX D: SPECTRE GUIDEWIRE INVESTIGATIONAL INSTRUCTIONS FOR USE

APPENDIX E: RAIDER GUIDEWIRE INVESTIGATIONAL INSTRUCTIONS FOR USE

APPENDIX F: WARRIOR GUIDEWIRE INVESTIGATIONAL INSTRUCTIONS FOR USE

APPENDIX G: BANDIT GUIDEWIRE INVESTIGATIONAL INSTRUCTIONS FOR USE

APPENDIX H: R350 GUIDEWIRE INVESTIGATIONAL INSTRUCTIONS FOR USE

## 1. Introduction

The purpose of this statistical analysis plan (SAP) is to outline the data handling methods and planned analyses to be used for the Teleflex CTO-PCI Study.

## 2. Abbreviations and Definitions

The abbreviations and definitions described below encompassed terminology utilized in this SAP and/or the corresponding CTO-PCI Clinical Study Protocol.

|        |   |
|--------|---|
| ACE    | Angiotensin converting enzyme                               |
| ACT    | Activated clotting time                                     |
| ADE    | Adverse device effect                                       |
| AE     | Adverse event   |
| ALT    | Alanine aminotransferase                                    |
| ARB    | Angiotensin receptor block                                  |
| AST    | Aspartate aminotransferase                                  |
| CABG   | Coronary artery bypass graft                                |
| CAD    | Coronary artery disease                                     |
| CEC    | Clinical events committee                                   |
| CFR    | Code of federal regulations (U.S.)                          |
| CHF    | Congestive heart failure                                    |
| CK     | Creatine kinase   |
| CK-MB  | Creatine kinase with M (muscle) and B (brain) subunits      |
| CRF    | Case report form  |
| (e)CRF | (electronic) case report form                               |
| CRO    | Contract Research Organization                              |
| CTO    | Chronic total occlusion                                     |
| CV     | Curriculum vitae  |
| EDC    | Electronic data capture                                     |
| FAS    | Full analysis set   |
| FDA    | Food and Drug Administration (U.S.)                         |
| GCP    | Good clinical practice                                      |
| GUSTO  | Global Use of Strategies to Open Occluded Coronary Arteries |
| HIPAA  | Health Insurance Portability and Accountability Act         |
| ICF    | Informed consent form                                       |
| ICH    | International Conference on Harmonization                   |
| IFU    | Instructions for use  |
| IRB    | Institutional review board                                  |
| ISO    | International Organization for Standardization              |

|      |  |
|------|--|
| MACE | Major cardiac adverse event                    |
| MDR  | Medical Device Reporting (to FDA)              |
| MI   | Myocardial infarction                          |
| NYHA | New York Heart Association                     |
| O.D. | Outer diameter                                 |
| PCI  | Percutaneous coronary intervention             |
| PI   | Principal investigator                         |
| PTCA | Percutaneous transluminal coronary angioplasty |
| PTFE | Polytetrafluoroethylene                        |
| SAE  | Serious adverse event                          |
| SAP  | Statistical analysis plan                      |
| TIMI | Thrombolysis in myocardial infarction          |
| UADE | Unanticipated (serious) adverse device effect  |
| ULN  | Upper limit of normal                          |
| URL  | Upper reference limit                          |

### **3. Study Design**

The study is a prospective, multicenter, single-arm, intent-to-treat, literature-controlled clinical study.

### **4. Randomization and Blinding**

The study is non-randomized and open-label.

### **5. Analysis Population**

Analyses will be conducted under the principles of intent-to-treat, using the full analysis set (FAS) as defined in ICH E9 (Statistical Principles for Clinical Trials). Primary analyses will include all available data on all enrolled subjects.

### **6. Objective**

The objective of this study is to evaluate angiographic confirmation of placement of any guidewire beyond the CTO, in the true vessel lumen, in patients undergoing CTO percutaneous coronary intervention (PCI) in which at least one Teleflex guidewire and at least one Turnpike catheter are used. The data captured in this study will be used to support FDA 510(k) clearance for a CTO indication.

## 7. ENDPOINTS

### 7.1. Primary Endpoint

The primary endpoint is defined as procedure success through discharge or 24 hours post-procedure, whichever comes first.

- Procedure success is defined as angiographic visualization of any guidewire in a position either distal or proximal to the occlusion depending on the route of access and the absence of in-hospital major adverse cardiac events (MACE).
  - In accordance with the study objective (Section 6), the definition of procedure success is to be interpreted as requiring presence of the guidewire in the *true vessel lumen*.
- MACE is defined as any serious adverse experience that includes cardiac death, target lesion revascularization, or post-procedural MI (Q-wave or non-Q-wave, with CK-MB > 3 URL).

### 7.2. Secondary Endpoints

- Frequency of successful recanalization (defined as angiographic confirmation of crossing the chronic total occlusion and restoring blood flow to the affected area).
- Frequency of MACE through discharge or 24 hours post-procedure, whichever comes first (in-hospital), and at 30 days post-procedure. The components of MACE will also be reported separately.
- Frequency of clinically significant perforation (defined as any perforation resulting in hemodynamic instability and/or requiring intervention including pericardiocentesis, embolization, prolonged balloon occlusion, stent graft, or comparable therapy).
- Procedural success according to crossing technique.
- Technical success.

## 8. General Statistical Considerations

The following general comments apply to all statistical analyses and data presentations.

### 8.1. Descriptive Statistics

Continuous data will be summarized using descriptive statistics: n, mean, standard deviation, standard error, median, and range or interquartile range. Discrete variables will be summarized using frequency counts and percentages. For ordinal-scaled variables, a combination of the following may be employed as appropriate: frequency and percentage of observations within a category and means and standard deviations of the scores of the categories.

### 8.2. Significance level

Unless otherwise specified, statistical analyses will be performed using one-sided hypothesis tests at an overall alpha level of 0.05.

### **8.3. Duration Variables**

Study Day 0 is the day of study device deployment (index procedure). Study day will appear in the listings where applicable and is calculated relative to day 0 using the general formula:

Study Day = (Date of Event – Date of Study Device Deployment)

Duration variables will be calculated using the general formula:

[(end date – start date)]

### **8.4. Missing Data**

All available data in the full analysis set will be used to evaluate study outcomes. Methods for replacing missing data such as last value carried forward or multiple imputation will not be routinely used.

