7.0 ENDPOINTS

7.1 Primary Endpoint

The primary endpoint for the study is procedure success through discharge or 24 hours post-procedure, whichever comes first. Procedure success is defined as angiographic visualization of any guidewire in a position either distal or proximal to the occlusion depending on the route of access and the absence of in-hospital major adverse cardiac events (MACE; defined in **section 14.0**).

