9.5 Schedule of Visits & Testing Requirements

Table 4 outlines the visits, visit windows, and testing requirements at each evaluation time point.

Table 4: Visits & Testing Requirements

Testing & Data Collection	Screening / Baseline	PCI Procedure (Within 30 days of Screening Assessment)	6-12 Hrs. Post-procedure	Discharge OR 18-24 Hrs. Post-procedure (whichever comes first)	30 days (± 7 days)
Inclusion and exclusion criteria	√				
Informed consent	√				
Demographics	√				
Medical & surgical history (within 14 days of procedure)	√				
Cardiac medication review	√	√		√	√
Pregnancy test (if female of child-bearing potential)	√				
Blood test (total CK and CK-MB)	√ ¹		√	√	
Angiogram (pre- and post-PCI)		√			
PCI procedure		√			
Adverse event monitoring		√	√	√	√
Device deficiency assessment		√			

¹ Must be obtained within 72 hours of the procedure.

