9.6.3 PCI Procedure

The PCI procedure will be performed with the study device(s) following these guidelines:

- At least one Teleflex guidewire and at least one Turnpike catheter must be used during a study PCI procedure
- The R350 guidewire should be used for all retrograde cases for which wire externalization is performed.
- The GuideLiner catheter or TrapLiner catheter should be used when any guide extension is necessary for completion of a study PCI procedure
- Additional study devices and commercially available guidewires and catheters may be used during a study PCI procedure at the discretion of the physician

Post-procedure angiographic imaging of the CTO must be captured and performed per the instructions provided by the core laboratory and must be captured in a precise manner as was used for the pre-procedure images. Angiographic images of the CTO must be sent to the core lab per specified method.

If the subject is returned to the procedure room and a guiding catheter is reinserted and a dilatation is performed, this will be considered a repeat intervention.

Standard PCI procedural data will be collected on the CRFs such as:

- Vessel and lesion characteristics
- TIMI grade flow pre and post treatment
- Approach technique(s)
- Type and size of devices used
- The order in which guidewires were used and which guidewire was the crossing guidewire
- Procedural durations including start/end times
- Air Kerma (Gy) and total fluoroscopy time
- Procedure-related medications
- Adverse event assessment including perforation and dissection classifications
- Device deficiency assessment

See **Section 14.0** for procedure-related definitions and **Table 5** below for recommendations for procedure-related medications.

Table 5: Procedure-Related Medications Recommendations

Timepoint	Medication Recommendations
Pre-procedure	
Aspirin: 100-325 mg non-enteric coated aspirin orally at least one hour and no more than 23 hours prior to procedure, or per hospital protocol.Clopidogrel: 300 mg loading dose the day before the procedure or 600 mg the day of the procedure or sufficient existing steady state blood concentration, or per hospital protocol. If the patient had been taking Clopidogrel (75 mg/day) for three or more consecutive days prior to the procedure, the loading dose need not be given. 
Note: The use of glycoprotein IIb/IIIa inhibitors is not recommended.

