10.2 Angiographic Core Laboratory

An angiographic core laboratory will be used to provide an unbiased assessment of angiographic imaging. The angiographic core laboratory will provide image acquisition and processing instructions to the sites. The angiographic core laboratory will follow its own Charter or similar procedure to systematize their image review in compliance with the study protocol.

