## 14. Revision History

| Revision | BRIGHT DCO#  | Effective Date | Revision Description   |
|----------|--|----------------|--|
| 1.0      | 2019-05-003  | 10 May 2019    | Initial Release  |
| A        | NA – Document now controlled via Sponsor's Agile document control system | 30 Jul 2019    | Revised section 9.1 and 11.3 to align with FDA recommendations provided at time of IDE approval.
Cover page and page header revision convention corrected from numerical to alphabetical. Document will now be controlled by Sponsor (via Agile system) vs. CRO document control. |

| Revision | BRIGHT DCO#  | Effective Date | Revision Description   |
|----------|--|----------------|--|
| B        | NA – Document now controlled via Sponsor's Agile document control system | 11 Feb 2020    | Updated a secondary objective and abbreviations related to changes made in the new protocol rev C.   |
| C        | NA – Document now controlled via Sponsor's Agile document control system | 17 Aug 2020    | Clarified the heading in section 6 to match the protocol and also clarified the primary endpoint (and procedure success definition) requiring presence of the guidewire in the true vessel lumen (as referenced in the study objective). This SAP is being clarified in lieu of an update to the protocol. |

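### Does the plan leave open how to score a subject whose true-lumen wire position was never confirmed?

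*SAP*

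**What the plan says.** The protocol (7.1, repeated in 14.0) defines the angiographic half of procedure success as "angiographic visualization of any guidewire in a position either distal or proximal to the occlusion depending on the route of access". The lumen is not mentioned there, but the protocol's objective in section 5.0 already asks for the wire to be in the true lumen. SAP 7.1 joins the two: "the definition of procedure success is to be interpreted as requiring presence of the guidewire in the" true vessel lumen. SAP section 14 dates this to Rev C of 17 Aug 2020 and explains that "This SAP is being clarified in lieu of an update to the protocol".

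On imaging, Protocol Table 4 schedules "Angiogram (pre- and post-PCI" and section 9.6.3 says that the post-procedure images follow the core laboratory's instructions, go to that laboratory, and "must be captured in a precise manner as was used for the pre-procedure images". The procedural data given as examples in 9.6.3 include "The order in which guidewires were used and which guidewire was the crossing guidewire", approach technique and TIMI flow before and after treatment. Section 10.2 says the core laboratory "will follow its own Charter or similar procedure to systematize their image review in compliance with the study protocol".

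On who is counted, SAP 5 applies intent-to-treat to all enrolled subjects, and SAP 10.1 assesses the endpoint for each of them. SAP 8.4 says "All available data in the full analysis set will be used to evaluate study outcomes" and rules out routine imputation. SAP 11 sizes the study on 135 evaluable subjects and plans for 150.

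**The concern.** The true-lumen condition reached the SAP about six months after Protocol Rev C (04 Feb 2020 to 17 Aug 2020), and the protocol's imaging and data-collection text was not revised to match. No passage specifies an image with the wire in position, the listed CRF examples do not name lumen position, and no sentence says outright whose read decides this component. The condition has substance: Protocol 2.0 describes wires passing the lesion by either a true-lumen or a subintimal route, so a wire seen beyond the occlusion is not automatically in the true lumen.

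Some subjects might therefore have a recorded crossing and no confirmed position. The endpoint definition would make them failures. The available-data wording, together with the undefined term evaluable in the sizing text, could be used to argue for leaving them out. The study is open-label with one decisive test, so a choice left until the counts are known could settle the result. If such subjects are in truth failures, leaving them out raises type I error; if they are in truth successes, failing them costs power.

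**Working it through.** **Inputs.** Performance goal 63.2%, postulated rate 73.2%, one-sided alpha 0.05, power 80%, 135 evaluable and 150 total (SAP 10.1 and 11). SAP 10.1 specifies exact binomial confidence limits; the matching exact binomial test is used here.

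**The plan's own figure.** The test passes with r or more successes, where r is the smallest count with P(X ≥ r) ≤ 0.05 for X ~ Bin(n, 0.632).

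- n=135: r=95, attained alpha 0.0491, power at 73.2% 0.8006. The planned 135 is reproduced.
- Normal approximation: n = [(1.645·√(0.632·0.368) + 0.842·√(0.732·0.268)) / 0.10]² = 135.96, in agreement.
- n=150: r=105, attained alpha 0.0487, power 0.836.

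**Effect of the scoring choice.** The planned rate gives 150 × 0.732 = 109.8, taken as 110. Let m of these 110 be unconfirmed. Counted as failures, the result is (110−m)/150; left out, it is (110−m)/(150−m).

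| m (assumed) | Counted as failures | p | Left out | p |
|---|---|---|---|---|
| 0 | 110/150 | 0.0056 | 110/150 | 0.0056 |
| 3 | 107/150 | 0.0224 | 107/147 | 0.0090 |
| 5 | 105/150 | 0.0487 | 105/145 | 0.0122 |
| 6 | 104/150 | 0.0690 | 104/144 | 0.0142 |
| 10 | 100/150 | 0.2139 | 100/140 | 0.0252 |
| 15 | 95/150 | 0.5232 | 95/135 | 0.0491 |

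The two scorings disagree at 110/150 only from m=6 to m=15. At m=16, leaving out also fails (94/134, p=0.0557).

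**Averaged over results.** With site-recorded successes X ~ Bin(150, 0.732), the chance that the scorings disagree is P(X ≥ c+m) − P(X ≥ 105+m), where c is the pass count for 150−m. This gives 0% for m=1, 5.6% for m=2, 11.9% for m=3, 20.4% for m=5 and 27.7% for m=6.

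**Type I error at a true rate of 63.2%.**

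- Every unconfirmed subject truly a failure, left out: the rate among the rest becomes 0.632·150/(150−m), and the error is 6.7%, 9.1% and 12.0% for m=2, 3 and 5.
- The same subjects counted as failures: 4.9% throughout.
- Missing status unrelated to outcome, left out, m=1 to 5: 3.8% to 4.9%.

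**Which scoring the text supports.**

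1. Success. SAP 7.1 adds the true-lumen condition expressly, so the protocol's shorter definition cannot be used to pass a subject without it. Even that definition asks for the wire to be seen on the angiogram, so a site's crossing record alone would not meet it.
2. Left out. SAP 10.1 covers each enrolled subject and SAP 5 covers all of them. SAP 8.4 says which data are used and does not remove anyone. Evaluable appears only where the sample size is discussed and defines no analysis population.
3. Non-success. Success is something that has to be shown. If it is not shown, the subject is not a success and remains among those enrolled. This follows from SAP 5, 7.1 and 10.1 read together.

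**Whose read.** Protocol 10.0 gives the core laboratory systematic image review as a guard against investigator bias, and 10.2 gives it the unbiased assessment of the angiograms. The component is angiographic, so the text points to that laboratory.

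**The case for a change.** The strongest case for a change is that the scoring is nowhere stated and the decision is fragile. Leaving out and failing can both be argued from the SAP alone, and they reverse the result at six unconfirmed subjects. The reversal does not depend on the exact test: at 104/150 the score test (p=0.0597) and the Wald test (p=0.0516) also miss 0.05. The core laboratory is to work in line with the protocol, whose success definition was not updated. A sentence in the SAP would cost little, and would be needed even if the Charter asks for the right image.

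The arithmetic stands, and so does the absence of an explicit scoring sentence. Three parts carry less weight. First, it cannot be said that wire position goes unrecorded: post-PCI imaging is scheduled under core-laboratory instructions and a Charter that are outside these documents, and the CRF items are only examples. Post-treatment TIMI flow is collected and may help in many cases, though no passage says that it settles lumen position. Second, the protocol's objective already required the true lumen, so a core laboratory working to the protocol is not working to a contrary aim. Third, the number unconfirmed is assumed. Six means 6/110 = 5.5% of recorded successes, all falling among the successes, and the inflated error rates need every one of them to be a true failure as well as the less natural scoring.

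The natural scoring has a price. If 1% of true successes cannot be confirmed, the success rate becomes 0.732 × 0.99 and power falls from 83.6% to 78.0%; at 2% it falls to 71.6%. That loss falls on the sponsor's chance of passing and does not make a false pass more likely.

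**Conclusion.** The concern does not call for a change to the plan. Followed as written, the SAP makes a subject without confirmed true-lumen position a non-success who stays in the denominator, and type I error remains at 4.9% with 105 of 150 needed to pass. The unwritten scoring sentence is a gap that analysts would fill in this way from SAP 5, 7.1 and 10.1, with the core laboratory as the reader of the angiograms. The difference between the protocol and SAP definitions is explained in the SAP's revision history and agrees with the protocol's own objective.

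The size is conditional. At 110/150, failing and leaving out give the same decision with five or fewer unconfirmed subjects and differ from six to 15; no expected count is given. The conclusion rests on reading SAP 8.4 as a statement about which data are used, with no power to remove subjects, and on the core-laboratory instructions, which are not available here, supporting a read of wire position. A clinical study report that stated the number unconfirmed would let any reader check the result against the figures above.

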8.2 Number of Sites & Subjects

The study will be conducted in up to 15 investigational sites in the U.S. This study will enroll up to 150 patients to provide adequate powering for hypothesis testing and an evaluable sample size of at least 135 patients. The study Sponsor and CRO will manage sites so that no single site enrolls more than approximately 20% of the total study enrollment.

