11.4 Adverse Event Relationship

The Investigator and the CEC will assess the relationship of the adverse event to the device treatment or procedure as follows:

- **Definitely:** The adverse event follows a strong temporal sequence to the receipt (or attempted receipt) of the device treatment or procedure. This can include an adverse event that occurs after the study procedure.
- **Probably:** The adverse event follows a reasonable temporal sequence to the receipt (or attempted receipt) of the device treatment or procedure, and the possibilities of other factors, such as underlying and concomitant illness, concomitant medications, or concurrent treatment can be excluded.
- **Possibly:** The adverse event follows a reasonable temporal sequence from receipt (or attempted receipt) of the device treatment or procedure and the possibility of device

treatment or procedure involvement cannot be excluded. However, other factors such as underlying or concomitant illness, concomitant medications, or concurrent treatment are presumable.

- **Unlikely:** The adverse event has an improbable temporal sequence to the receipt (or attempted receipt) of the device treatment or procedure, or it can be reasonably explained by other factors, including underlying or concomitant illness, concomitant medications, or concurrent treatment.
- **Not Related:** The adverse event has no temporal sequence to the interventional procedure, the device treatment, or any user handling, or it can be explained by other factors, including underlying disease or concomitant illness, concomitant medication, or concurrent treatment.

Adverse events adjudicated by the CEC as *definitely* or *probably* will be considered related adverse events for data analytic purposes. Events adjudicated by the CEC as *possibly*, *unlikely* or *not related* will not be considered related adverse events for data analytic purposes.

All reported major cardiac adverse events, regardless of relationship, will result in a procedure failure for data analytic purposes. Refer to **Section 14.0** for definitions of MACE and procedure success.

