Occlusion length 	Using good collateral images, try to measure "true" distance of occlusion, which tends to be shorter than the first impression.	Occl.Length  <20mm (0)  ≥20mm (1) point
Re-try lesion Is this Re-try (2 nd attempt) lesion? (previously attempted but failed)		Re-try lesion  No (0)  Yes (1) point
Category of difficulty (total point)		Total  points
 easy (0)  Intermediate (1)  difficult (2)  very difficult (≥3)		

Major adverse cardiac event (MACE): Any serious adverse experience that includes cardiac death, target lesion revascularization, or post-procedural MI (Q-wave or non-Q-wave, with CK-MB > 3 ULN). Classification of an event as a MACE will be performed by the CEC. [aligns with Asahi Intecc CTO-PCI, NCT02379923, which was based on Academic Research Consortium definitions; ref. Kandzari 2018]

Myocardial infarction (MI): Q-wave or non-Q-wave, with CK-MB > 3 ULN [*aligns with Asahi Intecc CTO-PCI, NCT02379923, which was based on Academic Research Consortium definitions; ref. Kandzari 2018*]

NYHA Heart Failure Classification [*Dolgin et al, 1994*]:

I	No limitation of physical activity. Ordinary physical activity does not cause undue fatigue, palpitation, dyspnea (shortness of breath).
II	Slight limitation of physical activity. Comfortable at rest. Ordinary physical activity results in fatigue, palpitation, dyspnea (shortness of breath).
III	Marked limitation of physical activity. Comfortable at rest. Less than ordinary activity causes fatigue, palpitation, or dyspnea.
IV	Unable to carry on any physical activity without discomfort. Symptoms of heart failure at rest. If any physical activity is undertaken, discomfort increases.

Perforation Classifications [*Ellis et al., 1994*]:

- **Type I:** Extraluminal crater without extravasation.
- **Type II:** Pericardial or myocardial blush without contrast jet extravasation.
- **Type III:** Extravasation through frank ($\geq 1\text{mm}$) perforation.

Procedure success: Angiographic visualization of any guidewire in a position either distal or proximal to the occlusion depending on the route of access and the absence of in-hospital major adverse cardiac events (MACE). [*aligns with Asahi Intecc CTO-PCI, NCT02379923; ref. Kandzari 2018*]

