## 10. Analysis of Study Endpoints

### 10.1. Primary Endpoint

The primary endpoint is procedure success through discharge or 24 hours post-procedure, whichever comes first. This endpoint will be assessed for each enrolled subject and presented as a proportion of successes with corresponding confidence limits calculated via the exact binomial method. Note that enrollment occurs when an investigational guidewire has entered the guide catheter.

Results will then be compared to a performance goal derived from the literature on comparable products in the intended study population. Formally, the hypotheses to be tested are as follows:

$$H_0: \mu \leq PG$$

$$H_A: \mu > PG,$$

where  $\mu$  is the proportion of successes and PG is the performance goal. The hypotheses will be tested at a one-sided alpha level of 0.05 and study success will be declared if the performance goal is met (i.e., if the null hypothesis above is rejected in favor of the alternative hypothesis).

Specific references and resulting analysis for the PG are as follows:

| Study              | Procedural Success % (n/N) | 95% confidence interval |
|--------------------|----------------------------|-------------------------|
| Olivari (2003)     | 73.3% (286/390)            | (68.6%, 77.7%)          |
| Prasad (2007)      | 69.7% (879/1262)           | (67.0%, 72.2%)          |
| Valenti (2008)     | 70.8% (344/486)            | (66.5%, 74.8%)          |
| Kandzari (2015)    | 79.0% (109/138)            | (71.2%, 85.5%)          |
| Kandzari (2018)    | 73.0% (119/163)            | (66.2%, 79.8%)          |
| Meta-analyzed rate | 73.2%                      |                         |

The meta-analyzed rate is derived from study-level pooling incorporating the five studies, with a resulting success rate of 73.2%. Incorporating a 10% statistical delta for hypothesis testing purposes, the performance goal for the primary endpoint is therefore PG = 63.2%.

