## 11. Determination of Sample Size

The postulated success rate for the primary endpoint is estimated to be 73.2%, based on the literature references cited above; the performance goal of 63.2% is as previously defined. Given a one-sided test at 0.05 alpha and desired power of 80%, the required evaluable sample size is 135. A study sample size of 150 total subjects therefore provides adequate powering for hypothesis testing as described above.

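### Does the SAP need a written rule for enrolled subjects whose primary outcome cannot be determined?

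*SAP*

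**What the plan says.** On missing data, SAP 8.4 uses what is available in the full analysis set and adds that "Methods for replacing missing data such as last value carried forward or multiple imputation will not be routinely used". SAP 5 is similar: "Primary analyses will include all available data on all enrolled subjects". Together they lean towards testing determined outcomes only. SAP 10.1 points the other way on the denominator: "This endpoint will be assessed for each enrolled subject". Protocol 7.3.1 and 7.3.3 carry the same pair of statements.

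The endpoint has two parts. SAP 7.1 states that "Procedure success is defined as angiographic visualization of any guidewire in a position either distal or proximal to the occlusion", with the wire in the true lumen, and adds the absence of in-hospital MACE. On MACE, Protocol 11.4 says "All reported major cardiac adverse events, regardless of relationship, will result in a procedure failure for data analytic purposes", and Protocol 14.0 says "Classification of an event as a MACE will be performed by the CEC".

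On size, SAP 11 says "the required evaluable sample size is 135", and Protocol 8.2 plans for up to 150 enrolled and "an evaluable sample size of at least 135 patients". Neither document defines the term.

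**The concern.** The study passes or fails on one proportion against a constant, so at the threshold the treatment of a single subject can decide it. The texts allow three treatments: drop the subject, score a failure, or score a success.

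Read literally, the two parts of the endpoint also handle gaps in opposite ways. Success needs a positive angiographic finding, so an unreadable film could be taken as a failure. The MACE part needs only that no event is on record, so a crossed subject with no post-procedure CK-MB could be taken as a success, although non-Q-wave MI is defined through CK-MB. In an open-label study, an unwritten rule could be settled after the results are known. SAP 9.1 tabulates missed visits and discontinuations, not undetermined primary outcomes.

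**Working it through.** **Inputs.** One-sided alpha 0.05, goal 63.2%, postulated rate 73.2%, 135 evaluable, 150 in total (SAP 10.1 and 11). The number undetermined, m, is not in the documents; I take 1, 2 and 5. In-hospital MACE among crossed subjects is not given either; I assume 2% to 10%. All p-values are exact binomial upper tails, P(X ≥ r | n, 0.632).

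**The plan's own figure.** With n = 135, 95 successes are needed: P(X ≥ 95 | 135, 0.632) = 0.0491, and power is P(X ≥ 95 | 135, 0.732) = 0.8006. So 135 reproduces, and 135/0.90 = 150. With all 150 determined, 105 are needed (p = 0.0487; 104 gives 0.0690) and power is 0.8359.

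**Confirmed successes needed under each rule**

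| m | Dropped | Scored failure | Scored success |
|---|---|---|---|
| 1 | 105 of 149 | 105 | 104 |
| 2 | 104 of 148 | 105 | 103 |
| 5 | 102 of 145 | 105 | 100 |

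**When the choice changes the result.** Probabilities are P(X = x | 150 − m, p) at p = 0.632, then 0.732.

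- m = 1, x = 104. Dropped: 104/149, p = 0.0550, fails. Scored success: 105/150, passes. Chance 0.0169 and 0.0463. Dropping and scoring as failure need the same 105, so they cannot disagree.
- m = 2, x = 104. Dropped: 104/148, p = 0.0432, passes. Scored failures: 104/150, p = 0.0690, fails. Chance 0.0139 and 0.0522.
- m = 2, x = 103. Dropped: 103/148, p = 0.0618, fails. Scored successes: 105/150, passes. Chance 0.0187 and 0.0441.
- m = 2, the two extreme rules against each other: 0.0139 + 0.0187 = 0.0326 and 0.0522 + 0.0441 = 0.0963.

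These chances are conditional on undetermined subjects occurring at all.

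**What each rule costs**

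*Dropped.* If the dropped subjects truly succeed at rate s and the overall rate is at the goal, the rate among those tested is (150 × 0.632 − s·m)/(150 − m).

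- Random loss (s = 0.632): type I error 0.0381, 0.0432 and 0.0432 for m = 1, 2 and 5; power at 73.2% is 0.8021, 0.8160 and 0.8088.
- Only crossed subjects lost (s = 0.90 to 0.98): type I error 2.2% to 3.6%.
- All lost are true failures (s = 0): m = 2 gives 94.8/148 = 0.6405 and type I error 0.0666; m = 5 gives 94.8/145 = 0.6538 and 0.1203.
- An intermediate case, s = 0.30 (assumed): 5.4% for m = 2 and 7.6% for m = 5.

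*Scored failure.* Power is P(X ≥ 105 | 150 − m, 0.732) = 0.8021, 0.7639 and 0.6257 for m = 1, 2 and 5. Under random loss, type I error falls to 0.0381, 0.0293 and 0.0122.

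*Scored success, crossed subjects only.* With q the MACE rate among crossed subjects, the apparent rate at the goal is 0.632 + (m/150)q. Over q = 2% to 10%, type I error is 4.9% to 5.1%, 4.9% to 5.2% and 5.1% to 5.8%.

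**The case for a change.** The strongest case for acting is that the plan leaves room for 15 non-evaluable subjects without saying who they are. At 15, a pass needs 95 confirmed successes if they are dropped (95/135), 105 if scored as failures, and 90 if scored as successes. Choosing among those bars after an open-label study would be a serious weakness, and a few sentences would close the gap.

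The absence of a written rule stands. The stakes do not follow from it, because 15 is headroom for sample size, not a forecast of loss. Protocol 9.6.3 makes post-procedure imaging mandatory, 9.6.4 and 9.6.5 each schedule CK-MB, 9.6.7 allows data gathered before withdrawal to be used, and 13.6 has all endpoint data monitored. The window ends at discharge or 24 hours, which leaves little time for loss.

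Nor is there one plainly right rule to write down. Dropping fits SAP 5 and 8.4 but, as shown, is not safe if unreadable films come mainly from failures. Scoring as failure fits SAP 7.1 and 10.1 and protects type I error, but costs power quickly. Treating a crossed subject without CK-MB as undetermined would add a laboratory condition to an endpoint that the protocol builds on reported events classified by the CEC.

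**Conclusion.** No change follows. The silence is a gap in detail that analysts can fill sensibly. Any known crossing failure or known MACE is a failure whatever else is missing, because success needs both parts. Only subjects with no known failure remain open. For those, the available-data wording supports a test on determined outcomes, and the proportion's denominator set against the number enrolled shows how many were left out. Any change made because of missing data must be described and justified under SAP 13, and Protocol 7.4 asks the same of departures from the planned methods.

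With one or two undetermined subjects, dropping and scoring disagree in about 1.4% to 5.2% of trials, depending on the true rate; the two extreme rules with two undetermined disagree in 3.3% to 9.6%. Which rule is better depends on why outcomes are missing, which the documents cannot tell us.

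This rests on undetermined outcomes being few, which the in-hospital window and the mandatory assessments support but no stated rate confirms. If five or more arose, mainly from unreadable angiograms, dropping them could no longer be called harmless, and the all-failure result over 150 would be the figure to look at.
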